#### Steady-state Assessment (Part 2):

Achievement of steady state concentrations during the multiple doses of TBAJ-876 will be assessed using Tukey's multiple comparison test at predose on all dosing days (Days 2-14) for each dose level separately.

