9.3 Statistical Analysis

Final statistical analyses will be performed using appropriate software, e.g. PhoenixTM WinNonlin[®] (Version 8.1 or higher, Certara, L.P. in conjunction with the internet-accessible implementation of Pharsight[®] Knowledgebase ServerTM [PKSO; Version 4.0.4 or higher, Certara, L.P.]) and SAS[®] (Version 9.4 or higher, SAS Institute Inc.).

For Parts 1, 2, and 3, PK parameters will be summarized by cohort using descriptive statistics. Summary statistics will also be presented by gender within each cohort.

For Part 1, dose proportionality for exposure parameters (C_{max} , AUCs) will be assessed using a power model approach. Food effect will be assessed using an analysis of variance (ANOVA) with food condition as the fixed effect.

For Part 2, dose proportionality for exposure parameters (C_{max} , AUCs) will be assessed using a power model approach. Steady state for each dose level will be assessed using an appropriate statistical methodology.

For Part 3, Food effect will be assessed using an ANOVA model with food condition as the fixed effect. The relative bioavailability analysis for the two strengths of TBAJ-876 tablets will be assessed using an ANOVA model with the strength of tablet administered under fasting conditions as the fixed effect.

Additional details will be provided in the SAP.

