- f. Vital signs (blood pressure, pule rate, temperature, respiration rate, and pulse oximetry) will measured at screening and check-in (Day -1). Vital sign measurements will be taken within 90 minutes prior to dosing and within 15 minutes of the defined time points at study hours 0, 1, 6, and 12 on Days 1 and 14. Furthermore, vital signs will also be taken once daily on Day 2 through Day 14 (6 hours after dosing) and once daily on Days 15-21 and Days 42, 63, 84, 105, and 126 and at early withdrawal (to be done within 15 minutes before review of medication and collection of adverse experiences). Both blood pressure and heart rate will be captured simultaneously. Blood pressure and heart rate will be measured after subjects are in a seated position for 2 minutes and then again after standing for 1 minute, except when they are supine or semi-reclined because of study procedures and/or adverse events, or as deemed necessary by the Investigator.
- g. AEs will be monitored from the time of signing the informed consent throughout the study via safety assessments, observation and participant reporting. Specific AE questions will be posed daily throughout the study until Day 21 and on all follow-up visits including a phone call on Day 133.
- h. TBAJ-876 or Placebo to TBAJ-876 Oral Suspension will be administered orally followed by 240 mL of water. Listerine® strips will be used as a blinding agent. A strip will be added to the subject's tongue before and after each dose.

Global Alliance for TB Drug Development

CONFIDENTIAL

- Dosing will only occur on Days 1-14.
- j. 12-lead safety ECGs will be printed and reviewed on-site by the Principal Investigator or designee. Triplicate ECGs will be completed at screening, Day -1, and on Day 15 or upon early withdrawal. All other time points will be single ECG readings. ECGs may be done within 2 hours prior to time of dosing and at 6 hours after dosing on Days 1, 2, 3, 8, 12, 14, and on Days 21, 42, 63, 84, 105, and 126. The predose ECG will be completed within 1 hour prior to the predose blood draw. If a participant experiences a postdose QTcF >500 ms or a change-from-baseline QTcF >60 ms, after repeat testing, additional ECGs should be recorded until normalization or return to baseline. All ECGs in Cohort 3 will be triplicate at each time point. In addition, subjects in Cohort 3 will have triplicate ECGs at 16 hours postdose on Day 1 and Day 14.
- k. Predose trough plasma samples will be drawn daily Days 1 through 14.

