This document is the property of Worldwide Clinical Trials Inc. and may not be duplicated, copied, altered or removed from company without prior approval from Worldwide Quality Assurance or in compliance with Worldwide Standard Operating Procedures.

Worldwide Clinical Trials Controlled Quality Management Document		
 WORLDWIDE CLINICAL TRIALS	Sponsor:	Global Alliance for TB Drug Development
	Protocol Number:	TBAJ-876-CL001
STATISTICAL ANALYSIS PLAN – PHASE 1		

parameters of  $AUC_{last}$ ,  $AUC_{inf}$ ,  $C_{max}$ ,  $T_{max}$ ,  $C_{last}$ ,  $T_{last}$ ,  $AUC_{Extrap\%}$ ,  $\lambda_z$ , and  $t_{1/2}$  will be calculated from plasma concentrations of TBAJ-876 (parent), M2 (metabolite), and M3 (metabolite); CL/F and  $V_z/F$  will be calculated for TBAJ-876 only.

Pharmacokinetic parameters will be summarized by cohort using descriptive statistics. Summary statistics will also be presented by gender within each cohort.

A power model approach will be used to assess of dose proportionality for Part 1 and Part 2.

For the assessment of the effect of food on TBAJ-876 and metabolites in Part 1, the 90% confidence intervals for geometric mean ratios, test-to-reference, of  $AUC_{0-72h}$ ,  $AUC_{0-14d}$ , and  $C_{max}$  will be determined as appropriate.

Achievement of steady state concentrations during the multiple doses of TBAJ-876 (Part 2) will be assessed using Tukey's multiple comparison test at predose on all dosing days (Days 2-14) for each dose level separately.

For Part 3, food effect will be assessed using an analysis of variance (ANOVA) model with food condition as the fixed effect. The relative bioavailability analysis for the two strengths of TBAJ-876 tablets will be assessed using an ANOVA model with the strength of tablet administered under fasting conditions as the fixed effect.

Additional pharmacokinetic parameters may be calculated if deemed appropriate.

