## 4 SAMPLE SIZE

For Part 1, 7 dose levels are planned. For 7 dose levels, 7 cohorts of 8 subjects will be used, 6 to receive active drug and 2 to receive placebo, all under fasting conditions.

QMD Ref: Worldwide-TMP-ST-006-4.0 Effective: 12Aug2019	Governing QMD: Worldwide-SOP-ST-001
Confidentiality Statement	

This document is the property of Worldwide Clinical Trials Inc. and may not be duplicated, copied, altered or removed from company without prior approval from Worldwide Quality Assurance or in compliance with Worldwide Standard Operating Procedures.

Worldwide Clinical Trials Controlled Quality Management Document		
 WORLDWIDE CLINICAL TRIALS	Sponsor:	Global Alliance for TB Drug Development
	Protocol Number:	TBAJ-876-CL001
STATISTICAL ANALYSIS PLAN – PHASE 1		

The effect of food on bioavailability of TBAJ-876 will be studied in a food-effect cohort comprised of two parallel groups, one fasting and the other fed. The fed group will enroll at least 10 subjects, which will yield complete data for at least 8 subjects if at most 2 fail to complete. For the fasted group, the data from the 6 subjects previously administered 100 mg TBAJ-876 in Cohort 4 (who have already completed the cohort) will be combined with data from 3 additional subjects to be enrolled in this fasted group. This will yield a complete data set for at least 8 subjects if at most 1 fails to complete. Thus, the total number of subjects planned is at least 60 to 70.

For Part 2, 39 subjects are planned to be enrolled. There are 3 cohorts planned. Cohort 1 with 12 subjects per cohort (9 to receive active drug and 3 to receive placebo). Cohort 2 with 13 subjects per cohort (9 to receive active drug and 4 to receive placebo), and Cohort 3 with 14 subjects per cohort (9 to receive active drug and 5 to receive placebo). All doses in Part 2 will be under fed conditions.

For Part 3, 30 subjects are planned to be enrolled. There are 3 groups planned with 10 subjects per group. All subjects will receive active drug under fasted or fed conditions.

Additional cohorts may be enrolled if it is deemed appropriate by the Sponsor to repeat a dose level, to study another dose level, or to increase cohort size (subject numbers).

The number of subjects selected for the study was based on the adequate number considered to provide sufficient safety data. This study has not been formally powered.

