### Food Effect (Part 1):

Statistical comparison of the PK parameters of TBAJ-876, M2, and M3 exposure ( $C_{max}$ ,  $AUC_{0-24h}$ ,  $AUC_{0-72h}$   $AUC_{last}$ , and  $AUC_{inf}$ ) will be performed using an Analysis of Variance (ANOVA) model for a 2-way crossover design on the ln-transformed data with treatment as the

QMD Ref: Worldwide-TMP-ST-006-4.0 Effective: 12Aug2019	Governing QMD: Worldwide-SOP-ST-001
Confidentiality Statement	

This document is the property of Worldwide Clinical Trials Inc. and may not be duplicated, copied, altered or removed from company without prior approval from Worldwide Quality Assurance or in compliance with Worldwide Standard Operating Procedures.

Worldwide Clinical Trials Controlled Quality Management Document		
 WORLDWIDE CLINICAL TRIALS	Sponsor:	Global Alliance for TB Drug Development
	Protocol Number:	TBAJ-876-CL001
STATISTICAL ANALYSIS PLAN – PHASE 1		

fixed effects and subject as a random effect. Conclusions regarding the results of the statistical analysis of PK parameters across treatments will be based on the ratio of the geometric means expressed as a percent (100×Fed/Fasted) and the 90% confidence interval about the ratio. A lack of food effect will be demonstrated if the 90% confidence intervals are fully contained within the limits of 80.00% to 125.00%.

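### The Part 2 steady-state test names Tukey's comparison of 13 trough days but no model, subject term or scale, although the same 9 active subjects per dose supply every trough

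*SAP*

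**What the plan says.** Protocol 9.3 leaves the method open: "Steady state for each dose level will be assessed using an appropriate statistical methodology", with further detail deferred to the SAP. The SAP gives that detail in one sentence, in 6.10 (Steady-state Assessment) and again in 3.1: Tukey's "multiple comparison test at predose on all dosing days (Days 2-14) for each dose level separately". It states no model, error term, scale, alpha or rule for declaring steady state.

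The data are repeated measures. Protocol Table 16, footnote k, reads: "Predose trough plasma samples will be drawn daily Days 1 through 14". SAP section 4 plans the same number of active subjects at each dose level:
- Cohort 1: "9 to receive active drug and 3 to receive placebo"
- Cohort 2: "Cohort 2 with 13 subjects per cohort (9 to receive active drug and 4 to receive placebo"
- Cohort 3: "Cohort 3 with 14 subjects per cohort (9 to receive active drug and 5 to receive placebo"

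Placebo plasma is not assayed (Protocol 9.1), so those 9 people supply every trough at a dose level.

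The SAP does not agree with itself on the days. Section 3.1 has troughs drawn on Days 1 to 14. Section 6.2.11 has them collected on Days 2 to 13, and its Day 14 list starts at 0.5 hours. The test needs Days 2 to 14.

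**The concern.** Whether troughs are still rising is a question about change within a subject. Tukey's procedure in its ordinary form compares independent group means. Applied to the 13 day means, it treats the 9 values on one day as unrelated to the 9 values on the next. The stable differences between subjects, which cancel when one day is compared with another in the same people, then count as noise. The test becomes too conservative, and because it looks for differences between days, the error runs one way: towards finding no difference too early in the dosing period.

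A rise is expected here. Protocol 1.7 reports model predictions of daily AUC increasing through 14 days of dosing, and Protocol section 3 plans around a terminal half-life of about 7 days. A programmer could follow the SAP sentence to the letter and run the weaker test. The protocol has no fallback specification.

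**Working it through.** The documents contain no figure to reproduce: no variance, alpha or detectable difference is given for this test. The check is therefore of consequence, under stated assumptions.

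**From the documents.** n = 9 active subjects per dose; k = 13 days (Days 2–14), giving 13 × 12 / 2 = 78 day pairs; half-life about 7 days.

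**Assumed.** Family-wise alpha 0.05; ln scale; the 7-day half-life governs accumulation; equal correlation between all days within a subject; between/within-subject CVs of 30/30%, 30/15%, 40/15% and 50/15%. With s² = ln(1 + CV²), the correlation sB²/(sB² + sW²) is 0.50, 0.79, 0.87 and 0.91.

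**Expected troughs.** The trough before the dose on day d is proportional to 1 − 2^(−(d−1)/7):
- Day 7: 0.448; Day 8: 0.500; Day 10: 0.590; Day 13: 0.695; Day 14: 0.724 of plateau.
- Day 14 over Day 7 = 0.724/0.448 = 1.62. Over Day 8 it is 1.45, over Day 10 it is 1.23, and over Day 13 it is 1.04.

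**Smallest ratio that Tukey can call different.**
- Day means only: exp{q × √[(sB² + sW²)/9]}, with 13 × 8 = 104 df and q = 4.796.
- With a subject term: exp{q × sW/√9}, with 12 × 8 = 96 df and q = 4.805.
- At 40/15%: sB² = ln(1.16) = 0.1484 and sW² = ln(1.0225) = 0.0223. Day means only: exp(4.796 × √(0.1707/9)) = exp(0.661) = 1.94. With a subject term: exp(4.805 × 0.1492/3) = exp(0.239) = 1.27. The first interval is 0.661/0.239 = 2.8 times as wide.

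**Simulation (20,000 runs per setting).** In each cell the first figure is for day means only and the second is with a subject term. The first day is the median of the first day from which no two remaining days differ.

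| CV between/within | Smallest ratio | Day 7 v 14 detected | Day 10 v 14 detected | First day |
|---|---|---|---|---|
| 30/30% | 1.94 / 1.60 | 15% / 53% | 0.2% / 3% | 7 / 8 |
| 30/15% | 1.69 / 1.27 | 40% / 100% | 0.3% / 33% | 7 / 10 |
| 40/15% | 1.94 / 1.27 | 15% / 99.9% | 0.1% / 32% | 6 / 10 |
| 50/15% | 2.21 / 1.27 | 5% / 100% | 0.0% / 33% | 6 / 10 |

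Repeat runs moved these detection rates by one or two points, so I quote about 5–41% against 53–100%. At 50/20% the rates for Day 7 v 14 were 4% and 96%.

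**Flat troughs.** Family-wise error is 0.2% at 30/30% and about 0% at the higher correlations when only day means are used, against about 5% with a subject term.

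**Limits.** Both versions detect Day 2 v Day 14 (ratio 0.724/0.094 = 7.7) in every run. Neither detects Day 13 v Day 14 (ratio 1.04) in as many as 1% of runs.

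**The case against.** The strongest reply is that the SAP does not prescribe a one-way analysis. Tukey's adjustment can equally be applied to day means from a model containing subject, and that would also fit the sentence. This stands: the defect is an unspecified model, and the figures above apply only if the ordinary test is run.

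Four stronger readings are tempting, and the documents do not support them.

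- **Deliberate omission.** A reader might infer this because the Part 1 food-effect paragraph in 6.10 names treatment as "fixed effects and subject as a random effect" and ln-transformed data. That paragraph describes a two-way crossover, while SAP sections 1 and 4 describe parallel fed and fasted groups, so it is a poor benchmark. The Part 3 paragraph also omits the log scale, yet Tables 14.4.13.1 to 14.4.13.6 are titled as log-transformed analyses. Silence in 6.10 is not proof of a choice.
- **A wrong steady-state day will be reported.** The SAP defines no such day. The title of Table 14.4.12.10 mentions only Tukey's test on trough concentrations.
- **Accumulation or later dosing depends on the result.** The accumulation ratios in SAP 6.2.12.2.2 are plain Day 14 over Day 1 ratios. CLss/F is calculated with no steady-state condition, although it is labelled as a steady-state quantity. No passage ties dose escalation to this test.
- **The rise would go unseen.** Troughs are also tabulated (14.4.5.1 and 14.4.5.2) and plotted as means (Figure 14.4.11) and by subject (Figure 14.4.17).

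It is also fair that a subject term does not cure reading non-significance as steady state. At a 7-day half-life the Day 10 trough is 59% of plateau and the Day 14 trough 72%, and the better test still cannot separate the last days.

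**Conclusion.** The point holds as a gap in specification with a material consequence under the literal reading. The one sentence that fixes the method permits two analyses that can give clearly different answers, and the one its wording most readily suggests ignores that 9 subjects supply all 13 troughs. On the assumptions stated, the loss in detecting Day 7 v Day 14 is from 53–100% down to about 5–41%. The first day without later differences comes one day earlier at 30/30%, and three to four days earlier at the higher correlations. A large shift therefore depends on CVs that the documents do not give.

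This is a secondary pharmacokinetic assessment in a study that was not formally powered, and the primary safety objective is untouched. The change is still worth making, because the better analysis uses the same data.

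**What to change.** In SAP 3.1 and 6.10, replace the sentence with wording such as: *Predose concentrations on Days 2 to 14 will be ln-transformed and analysed separately for each dose level, in a mixed model with day as fixed effect and subject as random effect (or a within-subject covariance). Day comparisons will be Tukey-adjusted at a stated family-wise alpha, and geometric mean ratios between days will be given with 90% confidence intervals.* State the alpha and how the comparisons will be read as evidence for or against steady state.

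Reconcile the trough days as well: Days 2–14 in the analysis (3.1 and 6.10), Days 2–13 collected in 6.2.11, and Days 1–14 drawn in 3.1 and in Protocol Table 16.

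The cost is a few lines of SAP text and one model statement in the program, with no new data. The small downside is that steady state will be reported later, or not at all, more often.

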#### Food Effect and Relative Bioavailability (Part 3):

Food effect will be assessed for TBAJ-876, M2, and M3  $C_{max}$  and AUCs using an ANOVA model for parallel study design with food condition as the fixed effect. The relative bioavailability analysis for the two strengths of TBAJ-876 tablets will be assessed for TBAJ-876, M2, and M3  $C_{max}$  and AUCs using an ANOVA model for parallel study design with the strength of tablet administered under fasting conditions as the fixed effect.

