Note: PK sampling for deciding to escalate to the next dose will be through the morning of Day 15, i.e., will include the profile on Day 14, and the dose escalation meeting will take place around Day 28 when interim PK data is available from the bioanalysis lab. Therefore, the dose escalation meeting and decision will be based on PK through the morning of Day 15 and approximately 28 days of safety data, depending on the turnaround time of the bioanalysis.

Subjects will continue to be dosed up to 14 days and be monitored for safety at timepoints indicated in the schedule of assessments (Table 16). After the last dose, subjects will remain in the clinic for 7 additional days and will then enter an additional follow-up period of 15 weeks or longer, if indicated by interim PK analyses.

During each cohort, blood samples will be obtained before each dose of study drug, and at serial timepoints postdose on Days 1 and 14. Samples will be taken according to the schedule provided in Table 16, with the last sample being obtained on Day 126, or possibly later if a decision is made to extend monitoring. Plasma PK samples will be analyzed for TBAJ-876, M2, and M3 using validated analytical methods. Appropriate PK parameters will be calculated using non-compartmental methods. In addition, blood and urine will be collected for clinical laboratory evaluations.

For Cohorts 2 and 3, an additional ECG extraction will occur at 16 hours postdose on Day 1 and Day 14. For Cohort 3, all ECGs performed will be triplicate ECGs at each time point listed in Table 15, including the additional 16 hour postdose time point. The sampling and safety assessment schedule may be revised based on what is learned about PK from Part 1 of the study and it may be further revised based on evolving data in Part 2.

Female subjects will have blood collected for serum pregnancy testing. Females claiming postmenopausal status will have blood collected to measure FSH levels.

Subjects who withdraw from the study will not be replaced.

Part 3:

Part 3 is a single-dose design study with 3 planned dose groups each consisting of 10 subjects.

Subjects will be assigned to one of 3 groups and dose:

- Group 1: TBAJ-876 100 mg (1 x 100 mg tablet) under fasted conditions.
- Group 2: TBAJ-876 -100 mg (1 x 100 mg tablet) under fed conditions.
- Group 3: TBAJ-876 100 mg (4 x 25 mg tablets) under fasted conditions.

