## 5 RANDOMIZATION

In Parts 1 and 2, each subject will receive an assigned treatment (active or placebo) based on the randomization schedule prepared by the unblinded statistician. The unblinded pharmacy staff will ensure compliance with the randomization schedule.

All subjects entering the Part 1 food-effect cohort will receive active drug (TBAJ-876 100 mg). In this food-effect cohort, new subjects will be enrolled in two parallel groups, one fasting (3 additional subjects) and the other fed (10 subjects).

For Part 3, all subjects will be randomly allocated to receive active drug under fasted or fed conditions.

QMD Ref: Worldwide-TMP-ST-006-4.0 Effective: 12Aug2019	Governing QMD: Worldwide-SOP-ST-001
Confidentiality Statement	

This document is the property of Worldwide Clinical Trials Inc. and may not be duplicated, copied, altered or removed from company without prior approval from Worldwide Quality Assurance or in compliance with Worldwide Standard Operating Procedures.

Worldwide Clinical Trials Controlled Quality Management Document		
 WORLDWIDE CLINICAL TRIALS	Sponsor:	Global Alliance for TB Drug Development
	Protocol Number:	TBAJ-876-CL001
STATISTICAL ANALYSIS PLAN – PHASE 1		

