### Baseline Characteristics

- Weight at Screening (kg)
- Height at Screening (cm)
- BMI at Screening (kg/m^2)

Contraceptive data collected from female subjects will be listed separately.

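### Part 3 ratios come from two separate unadjusted two-group ANOVAs, and the Part 1 food effect compares groups with no described random allocation; recorded body weight enters neither model

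*SAP*

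**What the plan says.** **Part 3.** SAP section 4: "There are 3 groups planned with 10 subjects per group". SAP 6.10 assesses food effect "using an ANOVA model for parallel study design with food condition as the fixed effect" and relative bioavailability "using an ANOVA model for parallel study design with the strength of tablet administered under fasting conditions as the fixed effect". SAP 3.1 and Protocol 9.3 give the same two one-factor models, with no covariate. On allocation, SAP section 5 says "For Part 3, all subjects will be randomly allocated to receive active drug under fasted or fed conditions", while Protocol section 3 says only "Subjects will be assigned to one of 3 groups and dose".

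**Part 1 food effect.** The groups are parallel. The fasted group combines "the data from the 6 subjects previously administered 100 mg TBAJ-876 in Cohort 4" with three newly enrolled subjects; the fed group is ten new subjects (SAP sections 4 and 5). The only Part 1 randomisation described is active against placebo. SAP 6.10 nevertheless writes the model as a two-way crossover ANOVA with a random subject effect. Protocol 9.3 has food condition as the only effect. Neither has a covariate. Absence of a food effect requires the 90% interval to lie within 80.00-125.00%.

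**Weight.** It is recorded at screening and check-in (Protocol 5.4 and 6.3). Entry requires at least 50.0 kg and a BMI of 18.5 to 32.0 (Protocol 5.1). In the SAP it appears in the baseline table (6.6), which is descriptive only, and in a listing (6.11.3); it is in no PK model.

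**The concern.** Every one of these comparisons is between different people, so all between-subject variation in exposure goes into the error term. A baseline variable that explains part of that variation is available for everyone and is unused. In Part 3 each contrast also estimates its variance from 20 subjects when 30 are available.

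The two parts carry different risks. In Part 3, if allocation is random, the stake is interval width. In Part 1 nothing described in the design balances fed and fasted subjects on weight, so the point estimate itself can be displaced, and that estimate is read against fixed limits.

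**Working it through.** The documents give no PK variability, no weight-exposure relation and no precision target (the study is stated not to be formally powered), so there is no figure to reproduce.

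**Inputs from the documents:** 10 per group in Part 3; 10 fed and 6 + 3 = 9 fasted in Part 1; 90% interval and limits 80.00-125.00% for Part 1. Part 3 has no stated interval level or limits; 90% is carried over.

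**Assumptions:** between-subject CV 30-50%; SD of ln(weight) 0.15-0.20; exposure proportional to weight^-0.75 to weight^-1. With s = sqrt(ln(1 + CV²)), the within-group correlation is r = exponent × SD / s. At CV 30%, s = 0.294, so r runs from 0.75 × 0.15 / 0.294 = 0.38 to 1 × 0.20 / 0.294 = 0.68. At CV 40% it is 0.29-0.52, and at CV 50% 0.24-0.42.

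**Part 3, cost if weight is irrelevant.** The planned half-width on the ln scale is t(0.95, 18) × s × sqrt(2/10). The three-group model with ln(weight) has 30 - 4 = 26 df and an expected variance inflation of 1 + 1/25 for estimating the weight slope. The ratio is (1.706/1.734) × sqrt(1.04) = 1.003. The estimated SD also averages slightly higher on 26 df than on 18, a further factor of about (1 - 1/104)/(1 - 1/72) = 1.004, giving about 1.007. Simulation of 3 × 10 subjects gives 1.006-1.007.

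**Part 3, gain if weight matters** (simulated mean 90% half-widths, ln scale):

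| CV | Planned pairwise ANOVA | Three groups + ln(weight) | Narrower by |
|---|---|---|---|
| 30% | 0.224 | 0.209 to 0.165 | 7-26% |
| 40% | 0.295 | 0.283 to 0.254 | 4-14% |
| 50% | 0.361 | 0.353 to 0.330 | 2-9% |

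Break-even is at about r = 0.12. Pooling three groups without weight accounts for about 1.3% of the narrowing.

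**Part 1, cost and gain.** There is no third group to pool. With 10 and 9 subjects the ratio at r = 0 is t(0.95, 16)/t(0.95, 17) × sqrt(1 + 1/15) = (1.746/1.740) × 1.033 = 1.037; simulation gives 1.035. Break-even is about r = 0.26. At r = 0.5 the interval is about 10% narrower.

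**Part 1, displacement.** If the fed group is 10% lighter, the unadjusted ratio is multiplied by 0.9^-0.75 = 1.082 to 0.9^-1 = 1.111, an upward shift of 8-11%. In simulation the mean ln ratio is 0.080-0.106 unadjusted and 0.001 adjusted.

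**What adjustment cannot do.** With 10 against 9, CV 40% and a true ratio of 100%, the chance that the 90% interval lies within 80-125% is about 0.4% unadjusted and 1.8% adjusted at r = 0.5. Weight does not make up for the sample size.

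**The case against.** The unadjusted ANOVA is a valid, protocol-specified analysis, and the gain from a covariate rests on a relation that the documents do not report. That stands. With exponent 0.5 and SD of ln(weight) 0.15, adding weight to a two-group model does almost nothing at CV 30% (×0.997) and widens the interval at CV 40% (×1.013) and 50% (×1.021). The very small cost in Part 3 depends on pooling. Against a pooled model without weight, the covariate costs about 2% if irrelevant, and pooling assumes equal log-scale variances in fed and fasted groups.

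Three stronger readings are tempting, and the documents do not support them.

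- A reader might infer that weight imbalance biases the Part 3 ratios. SAP section 5 says that Part 3 is randomly allocated. Chance imbalance is then sampling error that the interval already covers. The protocol's wording is weaker but does not contradict this.
- A reader might infer that the SAP ratio drives the MAD doses, because Protocol 1.7 uses the food-effect component. That section describes, in the past tense, a mathematical PK model and does not name the ANOVA ratio. The first two MAD doses were already in protocol version 8.0 (03 Dec 2021), before SAP version 2.0 (18 Apr 2022).
- A reader might infer that weight adjustment makes the Part 1 comparison sound. It cannot remove cohort or period differences between the Cohort 4 subjects and later enrolees.

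It also stands that the Part 1 food-effect data had been used in modelling before SAP 2.0. Replacing the planned ratio by an adjusted one at that stage would look data-informed, which favours showing both.

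**Conclusion.** The point holds as an inexpensive improvement, on two separate grounds.

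For Part 3 it concerns precision only and is conditional on a weight-exposure correlation. Under the assumptions above the 90% intervals would be 2-26% narrower, depending mainly on the CV; with no correlation they would be 0.6-0.7% wider.

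For Part 1 it concerns possible confounding. No fed/fasted randomisation is described, two thirds of the fasted group comes from an earlier cohort, and an assumed 10% weight difference would move the ratio by about 8-11% against margins of 20% and 25%. Whether such a difference exists is not known from the documents. The Part 1 model also needs rewriting in any case: with one value per subject, a crossover ANOVA cannot separate the random subject effect from residual error.

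**What to change.** - **SAP 6.10, Part 3** (and the matching text in 3.1): fit one model, ln(parameter) = group (three levels) + ln(screening weight). Report the Group 2/Group 1 and Group 3/Group 1 geometric mean ratios with 90% confidence intervals from it.
- **SAP 6.10, Part 1:** replace the two-way crossover model with a parallel-group model on the ln scale. Report the fed/fasted ratio with ln(screening weight) as a covariate next to the unadjusted ratio, and state beforehand which one is read against 80.00-125.00%.
- **SAP section 7:** record both changes, since it now says that there are none.

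The cost is a few lines of SAP text and one model term. If weight is unrelated to exposure, 90% intervals are about 0.6-0.7% wider in Part 3 and about 3.5% wider in Part 1. The pooled Part 3 model assumes equal log-scale variances. The Part 1 report should say that cohort and period differences remain unadjusted.
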